5.7.3.5 Use of Point-of-Care INR Devices

- When LMWH is co-administered with warfarin, LMWH may prolong the INR independent of the effect of warfarin. When the INR is measured in a laboratory, the potential INR-prolonging effect of LMWH is neutralized by adding a heparinase to the thromboplastin reagents used for INR testing.
- All LMWHs can prolong the INR, with dalteparin demonstrating an intermediate effect compared to other LMWHs. With therapeutic-dose dalteparin, the 3-hour post-dose INR is, on average, 0.72 INR units higher than the pre-dalteparin INR.
- Until recently, it had been difficult to add heparinase to test strips in point-of-care INR measuring devices to neutralize the effect of the heparin, though newer device strips may contain a heparinase.

- If a site (or an individual patient) uses a point-of-care device for INR management, it is recommended that one of the following 2 approaches is used while patients are receiving study drug:
 - If possible, substitute laboratory-based INR testing instead of point-of-care testing during the 1-2 week period when study drug is being administered before and after surgery/procedure.
 - If it is necessary to use a point-of-care INR device during the time when study drug is being administered, schedule INR testing so that the INR is measured **before a** scheduled injection of study drug (e.g., before AM dose of study drug); documentation of the use of a point-of-care INR is required in the electronic data system.

5.7.3.6 Patient Encounters 6, 7, and 8 (telephone contact: Day +8 to Day +29)

 Patients will have weekly telephone contact at Day +8 to Day +14; Day +15 to Day +21; Day +22 to Day +29 to assess for efficacy and bleeding outcomes.

5.7.3.7 Patient Encounter 9 (visit or telephone contact: Day +30 to +37)

- This patient hospital/clinic visit or telephone contact constitutes the end-of-study patient encounter.
- This encounter will include an assessment of efficacy and bleeding outcomes; other adverse outcomes and to complete and confirm data collection and retrieve unused study medication.
- For patients who are unable to have a hospital/clinic visit, information on study outcomes will be collected by telephone contact, and arrangements will be made for collection of unused study medication through alternative means.

5.8 Non-scheduled Patient Encounters and Final Patient Contact

- In patients who have any suspected or confirmed primary outcome event (ATE, major bleeding) occurring after randomization, this will necessitate documentation of the event in the EDC system within 24 hours after knowledge of the event.
- In patients who have any suspected or confirmed secondary outcome (acute coronary syndrome, venous thromboembolism, non-major bleeding) events after randomization, this will necessitate a non-scheduled patient encounter with a face-to-face hospital/clinic visit within 72 hours after the event.
- The final patient contact will occur on Day +30 to Day +37 to review possible study outcomes and collect any remaining unused study medication.

5.9 Summary of Trial Intervention, Procedures and Patient Follow-up

Preoperative protocol: patients will have an initial screening visit for the trial between Day -30 and Day -15

Study day

before the planned surgery/procedure. Eligible patients will be approached for study participation and written informed consent will be obtained.

- Patients will discontinue warfarin on Day -5 (with last dose on Day -6 before surgery/procedure) and will be randomly allocated to receive study drug, defined as either twice-daily dalteparin or twice-daily placebo.
- Study drug will start on Day -3 in the morning and will stop after the morning dose on Day -1. It is recommended that INR testing be done on Day -1 or Day 0 before the surgery/procedure.

Postoperative protocol: an assessment of hemostasis will be done on the day of the procedure (Day 0) and on subsequent days per protocol (depending on inpatient vs. outpatient status). Warfarin may be re-initiated within 24 hrs after surgery/procedure (**dark cross-hatched portion of warfarin bar**). Study drug (dalteparin/placebo) is re-initiated according to a pre-specified classification of procedure-related bleeding risk.

- For patients having a *minor surgery/procedure*, study drug will be initiated within 24 hours after the surgery/procedure when adequate hemostasis has been achieved; the first dose of study drug will be given on Day +1 (gray portion of study drug/placebo bar).
- For patients having a *major surgery/procedure*, study drug will be initiated 48-72 hours after the surgery/procedure when adequate hemostasis has been achieved; the first dose of study drug will be given on Day +2 or Day +3 (hatched portion of study drug/placebo bar).
- For patients with inadequate postoperative hemostasis, irrespective of the surgery/procedure classification, study drug may be withheld for up to 72 hours after the surgery/procedure (Day +3), after which time continuing to withhold study drug would constitute a protocol deviation. INR testing is recommended at least twice between Day +2 and Day +10. Any additional INR testing during the study period will be as per usual clinical practice. Study drug will be continued until the INR is ≥2.0.

Patient follow-up: Patients will be contacted at least weekly after the surgery/procedure to assess for efficacy, bleeding, and other adverse outcomes. Final contact will occur on Day +30 to Day +37 to assess for study outcomes or adverse events and collect any remaining unused study medication. Any suspected efficacy or bleeding outcomes that occur during the study period will necessitate a Patient Encounter (telephone or visit) and, if required, an unscheduled visit with study personnel for further clinical assessment and outcome documentation as required.

5.10 Endpoint Measurements

All endpoints will be analyzed using the modified intent-to-treat population (MITT). This is

CONFIDENTIAL

defined as all patients who have their warfarin discontinued (Day -5). The patients will be followed for at least 36 days (5 days pre-surgery/procedure + 1 day of surgery/procedure + 30 days post-surgery/procedure) or longer depending on whether the surgery/procedure was delayed and the date of Patient Encounter 9.

The primary endpoint of this trial (ATE, major bleeding) is defined based on criteria developed by consensus groups. The secondary endpoint of this trial is defined based on criteria developed by consensus groups or by criteria used in previous clinical trials.

- ATE, definitions are based on criteria established by the Stroke Council of the American Heart Association-American Stroke Association (stroke) [30], the Transient Ischemic Attack Working Group (TIA) [31], and the American Association for Thoracic Surgery (systemic embolism) [32].
- Major bleeding, definition is derived from criteria established by the Control of Anticoagulation Subcommittee of the International Society on Thrombosis and Hemostasis [33].

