5.7.2.1 Patient Encounter 4 (visit or telephone contact)

- All patients will undergo a postoperative assessment of hemostasis on the day of surgery/procedure (Day 0). This will consist of a hospital/clinic visit for patients undergoing an in-hospital surgery/procedure (e.g., cholecystotomy, endoscopy), and a telephone contact for patients undergoing an out-of-hospital surgery/procedure (e.g., dental extraction).
- The determination of adequate postoperative hemostasis will be based on the assessment by the Site Investigator and, when appropriate, in conjunction with the surgeon/interventionist.

Study drug dispensation (after surgery/procedure)

- In patients who *did* receive study drug for postoperative administration during a preoperative visit, no additional dispensing of study drug will be required. Patients will be given instructions in regard to postoperative administration of study drug.
- In patients who did not receive study drug for postoperative administration during a preoperative study visit, study drug will be dispensed for the postoperative period. Patients will be given instructions in regard to postoperative study drug administration.

Potential Delay or Cancellation of Surgery/Procedure

It is anticipated that a small proportion of study patients will have their surgery/procedure delayed or cancelled, for example, because of operating room unavailability or an intervening medical illness. In such cases, the following protocol will be followed:

- For patients having the surgery/procedure delayed for ≤ 3 days after the originally scheduled surgery/procedure date (i.e., ≤ 3 days after Day 0), such patients will remain in the study and will continue to have study drug administered according to the study protocol until the morning of the day prior to the rescheduled surgery/procedure. The rescheduled surgery/procedure date will be considered Day 0 for the study. Such patients will continue to be followed through Patient Encounter 9 and efficacy and safety data will be collected.
- For patients having the surgery/procedure delayed for >3 days (or cancelled) after the originally scheduled surgery/procedure (i.e., >3 days after Day 0), in such patients

study drug will be discontinued and the patient will be managed according to the local investigator's usual practice. Such patients will continue to be followed through Patient Encounter 9 and efficacy and safety data will be collected.

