- *For patients having a major surgery/procedure*: They will have delayed initiation of study drug after the surgery/procedure. **The first dose of study drug will be** administered on Day +2 or Day +3, not earlier than 48 hours after surgery/procedure and not later than 72 hours after the surgery/procedure, and when adequate hemostasis has been achieved.
 - In some patients with prolonged inadequate hemostasis, irrespective of the type of surgery/procedure, study drug may be withheld for up to 72 hours after surgery/procedure (Day +3). Withholding study drug for more than 72 hours after surgery/procedure will constitute a protocol deviation.

5.7.3.3 Patient Encounter 5 (hospital /clinic visit or telephone contact: Day +1 to Day +7)

CONFIDENTIAL

All patients will have at least one scheduled hospital/clinic visit or telephone contact between Day +1 and Day +7 to assess for efficacy and bleeding outcomes. Hospital or clinic visit is to be preferred over telephone contact.

Individual sites that practice remote patient management may use the telephone encounter option. If this approach is used:

- Patient contact must be made directly by study personnel (i.e., not through clinic staff managing the patient).
- The interview must be thorough and cover all symptoms that might be related to efficacy or bleeding outcomes for the study, particularly any non-major bleeding symptoms.

If the patient endorses any symptoms that might represent an efficacy and/or major safety outcome, (Section 5.10 Endpoint Measurements), the research coordinator would need to evaluate the patient in person for this specific patient encounter. Non-major bleeding symptoms will be reviewed with the site P.I. to determine if the patient needs to be evaluated in person*

Any additional patient encounters will be in accordance with usual clinical practice.

5.7.3.4 INR testing

- The BRIDGE trial recommends that INR testing after surgery/procedure is done at least twice between Day +2 and Day +10.
- In regard to the frequency of INR testing beyond that recommended by the trial protocol, this will be determined by the Site Investigator **as per usual clinical practice.**
- The site and manner of INR testing will be done in accordance with patients' usual practice, which includes testing done at a hospital-based laboratory, a clinic-based laboratory, a free-standing (i.e., private) laboratory, or by a point-of-care (portable) INR measuring device.

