5.12.1 Primary efficacy endpoint analysis

The primary efficacy outcome is ATE, defined by one or more of the following events occurring within the time period specified above:

- ischemic stroke
- transient ischemic attack
- systemic embolism

If the patient dies before day 35 and has not had the primary event, then it will be assumed that the patient would not have had an event had he/she been followed for 35 days.

The primary endpoint analysis is a non-inferiority analysis with an absolute margin of 1.0 percent. For that reason, the statistical test must provide confidence limits for the difference in rates. The two tests available with standard software that provide corresponding confidence limits are the likelihood ratio test and Barnard's test. The likelihood ratio test does not maintain the nominal alpha level for small sample sizes, and so that test will not be used.

There is a proposed an unconditional exact test based on a minimax elimination of the nuisance parameter [38]. The reference set was defined to be the set of all 2 x 2 tables with fixed row margins and all possible column margins. The test and its associated 95 percent confidence limits will be calculated using the StatXact 7 software [39]. If the upper 95 percent confidence limit for the difference in event rates (placebo primary event rate - bridging anticoagulation primary event rate) is less than 0.01, then the primary endpoint will have been met for placebo.

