7.2 Antithrombotic Prophylaxis against Postoperative Deep Vein Thrombosis (DVT)

The use of additional anticoagulants for prophylaxis against DVT, such as low-dose UFH (*e.g.*, UFH, 5000 units twice-daily) and low-dose LMWH (e.g., enoxaparin, 30 mg twice-daily), will be

CONFIDENTIAL

considered a protocol violation, as all patients will receive warfarin after surgery for prophylaxis against postoperative DVT.

In the 2008 ACCP Antithrombotic Consensus Guidelines, warfarin therapy (INR range: 2.0-3.0) was deemed effective in preventing DVT after hip or knee replacement and is given a Level 1A recommendation for use as DVT prophylaxis in these high-risk patients [27]. It is likely, therefore, that warfarin will also be effective in preventing DVT in lower-risk patients who are participating in this trial and are undergoing other types of surgery.

The use of mechanical devices for prophylaxis against DVT such as anti-embolic stockings or intermittent pneumatic compression devices will be allowed as this will not impact on the primary trial efficacy and bleeding outcomes (ATE, major bleeding). 7.3 Clinical Indication for Therapeutic Anticoagulation

Patients who are randomized to study drug and subsequently develop a need for therapeutic-dose anticoagulant therapy (e.g., acute coronary syndrome) will have study drug discontinued, and will receive therapeutic-dose anticoagulation as clinically indicated.

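### ATE non-inferiority is tested only in the MITT set, and no supportive analysis shows how far departures from assigned treatment have narrowed the contrast

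*Combined protocol and SAP*

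**What the plan says.** Section 5.10 names one population for every endpoint: "All endpoints will be analyzed using the modified intent-to-treat population (MITT"). It is "defined as all patients who have their warfarin discontinued (Day -5"). Neither a dose of study drug nor having the procedure is required.

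Section 5.12.1 then says "The primary endpoint analysis is a non-inferiority analysis with an absolute margin of 1.0 percent". The decision rule begins "If the upper 95 percent confidence limit for the difference in event rates" and requires that limit, for placebo minus bridging, to lie below 0.01. No second population is named. The only sensitivity analysis (5.12.6) is a time-to-event analysis that censors incomplete follow-up.

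The protocol lets study drug stop while outcomes are still collected:
- Procedure cancelled or delayed by more than 3 days (5.7.2.1): "study drug will be discontinued and the patient will be managed according to the local" investigator's practice, with follow-up to Encounter 9.
- After an efficacy or bleeding outcome, at the investigator's discretion (5.10.5).
- New need for therapeutic anticoagulation (paragraph at the end of 7.2): such patients "will have study drug discontinued, and will receive therapeutic-dose anticoagulation as clinically indicated".
- Suspected or proven heparin-induced thrombocytopenia (7.3).

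Other conduct is labelled but not linked to any analysis. Section 5.7.3.2 says "Withholding study drug for more than 72 hours after surgery/procedure will constitute a protocol deviation", and 7.2 classes added prophylactic heparin as a violation.

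**The concern.** In a superiority test, departures from assigned treatment usually make a positive result harder to reach. In a non-inferiority test they can make it easier, because two arms treated more alike have more similar event rates. The case the test must guard against is that no bridging is truly worse. In that case, bridging patients who do not get dalteparin, or placebo patients who do get an anticoagulant, pull the MITT difference below its value under the assigned strategies.

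Section 2.0 says the trial must show that omitting bridging does not bring a clinically important rise in ATE. From MITT alone, a reader cannot tell whether a small difference means little harm or little contrast, and the supplied text plans nothing that would help to separate the two.

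**Working it through.** **Inputs.** Bridging ATE rate 1.0%, no-bridging rate 1.0%, margin 1.0%, 80% power, two-sided alpha 0.05 and 1,641 per arm come from 5.11. Planned enrolment of 1,813 per arm comes from the synopsis. The dilution fraction f is assumed, because the documents give no rate.

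**The plan's own figure.** The simple formula gives n = (1.960 + 0.842)² × 2 × 0.01 × 0.99 / 0.01² ≈ 1,555 per arm, not 1,641. Summing binomial probabilities at 1,641 per arm gives 80.3% power for the likelihood ratio test and about 78% for an exact unconditional score test. The stated size is therefore consistent with 80% power, and the sample size is not the fault here.

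**Dilution model.** Take true rates at the margin: placebo 2.0%, bridging 1.0%.
- Placebo arm diluted: placebo rate = (1 − f) × 2.0% + f × 1.0%.
- Bridging arm diluted: bridging rate = (1 − f) × 1.0% + f × 2.0%.

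Either way the MITT difference is (1 − f) × 1.0%. For example, f = 20% gives 1.8% against 1.0%, a difference of 0.8 points. Put the other way, the effective margin on the undiluted difference is 1.0%/(1 − f): 1.11% at f = 10% and 1.25% at f = 20%.

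**Chance of a false claim.** Sum Bin(x; n, placebo rate) × Bin(y; n, bridging rate) over all outcome pairs (x, y) for which the test declares non-inferiority. The test used is the unconditional exact test with the score statistic (x/n − y/n − 0.01)/SE, where SE is estimated under a true difference of 0.01. The critical value is set so that the worst-case one-sided error is at most 0.025. The score ordering is an assumption, since 5.12.1 specifies an unconditional exact test without naming the statistic.

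| f (assumed) | 1,641 per arm, placebo diluted | 1,641, bridging diluted | 1,813, bridging diluted |
|---|---|---|---|
| 0% | 2.4% | 2.4% | 2.4% |
| 5% | 3.1% | 3.1% | 3.2% |
| 10% | 4.1% | 4.0% | 4.1% |
| 20% | 6.6% | 6.4% | 6.6% |
| 30% | 10.4% | 9.5% | 10.0% |

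A repeat enumeration agreed to within 0.1 point. With the placebo arm diluted at 1,813 per arm the values are slightly higher, at most about 11.5% at f = 30%. A larger trial does not remove the effect.

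**Direction.** The sign depends on the truth. For illustration, if placebo were better by 0.5 points, 20% dilution would move the difference from −0.5 to 0.8 × (−0.5) = −0.4, closer to the margin and so against the claim.

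**Power of a supportive analysis.** At 1.0% in both arms, starting from 1,813 per arm and excluding 0, 5, 10, 15 or 20%, exact power is about 82, 80, 78, 75 and 73%.

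**The case against.** MITT suits the question asked. Section 5.1 compares two management approaches, and 4.3 argues that postoperative flexibility is needed for the result to apply in practice. A restart delay of up to 72 hours is part of the regimen. This stands, and is why MITT should remain primary.

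Several stronger readings are tempting, and the documents do not support them:
- *That all the departures are permitted.* Withholding beyond 72 hours is a deviation and prophylactic heparin a violation. Only the four routes listed first above are allowed.
- *That every departure makes the arms alike.* Not restarting a saline injection changes nothing. Stopping drug after a first ATE cannot dilute that event. Prophylactic heparin is low-dose, and 3.4 says heparins are unproven against cardioembolic stroke, so giving such a patient the full bridging risk is an assumption.
- *That many patients will lack a contrast.* No rate is stated, and 5.7.2.1 expects delay or cancellation to be uncommon. The earlier cohorts in 4.3 had about 10% given no LMWH after surgery in two studies and 17% given a reduced postoperative dose in another. They included different patients, and partial omission dilutes less than full crossover.
- *That the bias always favours placebo.* Section 5.11.1 calls placebo superiority plausible, and dilution would then work against the claim.

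A per-protocol set also has its own bias. Requiring restart within 72 hours conditions on postoperative hemostasis, which preoperative dalteparin may affect. Section 5.11.1 describes the pathway from bridging to bleeding, longer warfarin interruption and ATE. Excluding those patients could remove ATE that bridging itself caused. This stands and shapes the fix.

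Finally, 9.5 mentions a statistical plan for sign-off, so the gap is established only for the supplied text.

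**Conclusion.** The gap is real and of moderate importance. In the supplied text the ATE non-inferiority claim rests on one population, and no planned analysis looks at adherence. If no bridging is truly worse by the full margin, 5% dilution raises the one-sided false-claim rate only from about 2.4% to 3.1%. At 10 to 20% it is about 4 to 7%, and at 30% about 10%. These figures depend on an assumed departure rate and on diluted patients taking on the other arm's full risk, so they show sensitivity and do not predict this trial's error rate. The point does not show that MITT is the wrong primary set, that the sample size is wrong, or that a non-inferiority finding would be false.

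**What to change.** Keep MITT as the primary analysis. Add a paragraph pre-specifying a supportive per-protocol or on-treatment non-inferiority analysis of ATE, with the same 1.0% margin and exact confidence limits. Base membership on rules already in the protocol, and fix it before unblinding. Exclude patients who:
- did not have the procedure within 3 days of schedule;
- did not take the assigned preoperative study drug; or
- received non-study therapeutic or prophylactic heparin before an event.

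Do not exclude patients whose study drug was withheld or stopped for bleeding or inadequate hemostasis, or else report the result with and without them. Tabulate departures by arm and type, so that readers can judge the actual dilution. State whether the two analyses agree, and call non-inferiority robust only if they do.

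The cost is one paragraph and one further analysis, provided the data exist. Section 5.7.3.7 retrieves unused medication, but the text does not say that the eCRF records individual study-drug doses or non-study heparin, and the sponsor should confirm this. The added set is not fully protected by randomisation, and it loses the power shown above, so a failure to meet the margin there needs cautious reading.

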5.10.1 Primary efficacy endpoint

The primary efficacy endpoint is ATE, defined by one or more of the events listed below.

1) Ischemic stroke (*either* criterion must be satisfied) [30]:

- any new, focal neurologic deficit that persists for >24 hours, OR
- any new, focal neurologic deficit of any duration and with evidence of acute infarction on computed tomography (CT) or magnetic resonance imaging (MRI) of the brain
- 2) Transient ischemic attack (*both* criteria must be satisfied) [31]:
 - any brief neurologic deficit caused by focal brain or retinal ischemia, with clinical symptoms lasting, typically, for <1 hour and not for >24 hours
 - no evidence of acute infarction on CT or MRI of the brain

3) Systemic embolism (*all three* criteria must be satisfied) [32]:

- symptomatic embolic episode associated with abrupt arterial insufficiency to the upper extremity, lower extremity or abdominal visceral organ
- verified by intraoperative or radiologic evidence (*e.g.*, CT angiography) of arterial occlusion
- occurs in the absence of other likely mechanisms (*e.g.*, atherosclerosis)

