5.10.3 Secondary efficacy endpoints

1) Acute myocardial infarction (ST- and non-ST-elevation) [34]

- typical rise and gradual fall (cardiac troponin) or more rapid rise and fall (creatine kinase-MB) of biochemical markers of myocardial necrosis to at least twice the upper limit of the normal range, with at least one of the following:
 - ischemic symptoms
 - development of pathologic Q-waves on the electrocardiogram (ECG)
 - ECG changes indicative of ischemia (*e.g.*, ST-segment elevation or depression)
 - > coronary artery intervention (*e.g.*, coronary angioplasty)
- 2) Deep vein thrombosis (both criteria must be satisfied) [35, 36]:
 - symptomatic venous thrombosis (lower or upper limb deep veins, or intraabdominal veins)
 - verified by non-compressibility on venous ultrasound or intraluminal filling defect on venography

3) Pulmonary embolism (both criteria must be satisfied) [37]:

- symptoms of thrombosis of the pulmonary arteries
- verified by high-probability ventilation-perfusion lung scan or intraluminal filling defect on CT angiography, or intraluminal filling defect pulmonary angiography or a non-diagnostic ventilation-perfusion lung scan with positive testing for deep vein thrombosis as defined above

4) Death

death of any cause based on autopsy findings or other medical records.

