9.6 Clinical Event Classification (CEC) Committee

The CEC Committee will be an independent committee with no direct involvement in the day-today undertaking of the trial. The overall responsibility of the CEC Committee is to provide an independent and blinded adjudication of the primary efficacy and safety outcomes as well as all cause deaths.

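### A systemic embolism proven only at autopsy cannot count toward the primary ATE endpoint, and autopsy-only PE, DVT and MI are lost in the same way; the effect is probably small but leans toward non-inferiority

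*Combined protocol and SAP*

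**What the plan says.** **Primary endpoint.** ATE is ischemic stroke, TIA or systemic embolism (section 5.10.1). The third is headed "Systemic embolism (*all three* criteria must be satisfied"), and one of its criteria is that the occlusion be "verified by intraoperative or radiologic evidence". CT angiography is given as an example of radiologic evidence.

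**Secondary endpoints (section 5.10.3).**
- PE is headed "Pulmonary embolism (both criteria must be satisfied"): symptoms, plus proof that is "verified by high-probability ventilation-perfusion lung scan" or comes from CT angiography, pulmonary angiography, or a non-diagnostic scan with a positive DVT test.
- DVT needs symptoms plus non-compressibility on ultrasound or "intraluminal filling defect on venography".
- MI needs a "typical rise and gradual fall (cardiac troponin) or more rapid rise and fall (creatine kinase-MB) of biochemical markers" to at least twice the upper limit of normal, plus one further sign.
- Autopsy is named only under Death.

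**Handling of deaths.** Section 5.12.1 covers this case: "If the patient dies before day 35 and has not had the primary event", the patient is taken as event-free. The time-to-event sensitivity analysis in section 5.12.6 censors the same patient at death.

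**Bleeding.** Section 5.10.2 lists fatal bleeding as its own route into major bleeding.

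**Adjudication.** Section 9.6 gives the CEC "independent and blinded adjudication of the primary efficacy and safety outcomes" and of all deaths.

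**The concern.** Take a patient who dies of bowel infarction without imaging or surgery, and whose autopsy shows a mesenteric embolus. The verification criterion fails, so the event is not ATE. The primary analysis then scores the death as a non-event, and the sensitivity analysis does not recover it. A patient who bled to death would count in the primary bleeding endpoint. The plan does not explain the difference.

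The direction matters because the primary test uses a fixed absolute margin of 1.0 percentage point. If the same share of true events goes uncounted in both arms, the observed difference shrinks while the margin stays put, which makes non-inferiority easier to declare. For PE, DVT and MI nothing confirmatory is at stake, but their reported rates would omit events proven only at autopsy.

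**Working it through.** **1. The definitions side by side**

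| Event | Endpoint | Accepted proof | Autopsy or fatal route |
|---|---|---|---|
| Systemic embolism | Primary | Surgery or imaging | None |
| PE | Secondary | Scan, angiogram, or scan plus DVT test | None |
| DVT | Secondary | Ultrasound or venography | None |
| MI | Secondary | Marker rise and fall plus one sign | None |
| Major bleeding | Primary (bleeding) | Several | Fatal bleeding |
| Death | Secondary | Autopsy or other records | Yes |

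Ischemic stroke needs no test if the deficit lasts more than 24 hours, so the closed proof list does not govern it in the same way. A related gap remains: a stroke fatal within 24 hours without CT or MRI meets neither stroke criterion.

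**2. The plan's own sample size**

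Inputs from section 5.11: 1.0% ATE in each arm, margin 1.0%, 80% power, two-tailed alpha 0.05 (0.025 on the tested side). The stated result is 1,641 per arm. Enumerating every pair of binomial counts at n = 1,641, the likelihood-ratio test has 80.3% power, which reproduces the figure. A score test has 77.8%. The synopsis plans 1,813 per arm.

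**3. How few events decide the result**

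Expected events per arm: 1,641 × 0.01 = 16.4. One event moves the difference by 1/1,641 = 0.061 points. With 16 bridging events, the upper limit of a two-sided 95% score interval stays below 1.0% for up to 19 placebo events at 1,641 per arm, and up to 21 at 1,813. The score interval stands in for the planned exact interval.

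**4. Effect of uncounted events**

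Let s be the share of all true ATEs provable only at autopsy, equal in both arms. The documents do not give s; it is an assumption. With true rates at the margin (2% placebo, 1% bridging), the observed rates become 0.02(1 − s) and 0.01(1 − s), so the observed difference is 0.01(1 − s). At s = 5% that is 0.0095.

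The test statistic is Z = (p_placebo − p_bridging − 0.01)/SE, with SE from the rates fitted under a difference of exactly 0.01. Non-inferiority is declared if Z ≤ −c, where c is set so that the maximum exact error is at most 0.025 (c = 1.959 at 1,641; 1.956 at 1,813). The chance of a false declaration is the sum of Bin(x; n, 0.02(1 − s)) × Bin(y; n, 0.01(1 − s)) over all pairs (x, y) meeting that rule.

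| s | Events lost per arm at a 1% rate (16.41 × s) | False non-inferiority, 1,641 per arm | 1,813 per arm |
|---|---|---|---|
| 0 | 0 | 2.4% | 2.4% |
| 1% | 0.16 | 2.5% | 2.5% |
| 2% | 0.33 | 2.7% | 2.7% |
| 5% | 0.82 | 3.1% | 3.2% |
| 10% | 1.64 | 4.0% | 4.2% |

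The error rises steadily with s but stays close to nominal unless s is appreciable.

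**The case against.** The strongest reply is that the affected case is narrow. The event must be a systemic embolism that is fatal, never imaged, never operated on, autopsied, and shown to be embolic. Suppose, purely for illustration, that systemic embolism is 5-20% of ATEs and 5-30% of those are provable only at autopsy. The loss is then 16.41 × 0.05 × 0.05 = 0.04 to 16.41 × 0.20 × 0.30 = 0.98 events per arm, or 0.25-6% of ATEs. That is well short of the three or four extra placebo events on which the verdict turns. This stands, and it limits the size of the point.

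It is also fair that the Manual of Procedures or a CEC charter, neither of which is in these documents, might already accept autopsy. The definitions cite outside consensus criteria as well. But the protocol's own text requires every listed criterion, and nothing in section 9.6 lets the CEC set one aside.

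Several stronger readings are tempting, and the documents do not support them:
- *Every fatal event found at autopsy is lost.* An event also shown by imaging, surgery or markers before death qualifies, and the death counts under Death.
- *The trial always knows the cause of death.* No section mandates autopsy, and section 5.10.3 allows other medical records.
- *The MI and PE loss can be sized.* The documents give no rates. Counting deaths that precede the required tests would not count deaths proven at autopsy. The MI wording can also be read as describing a marker pattern rather than requiring an observed fall.
- *Abdominal vein thrombosis seen on CT is excluded from DVT.* That concerns patients tested in life and turns on whether venography includes CT venography, which the text leaves open.

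**Conclusion.** The gap is real on the written text. An event proven only at autopsy fails the definition of systemic embolism, PE, DVT or MI. For systemic embolism, sections 5.12.1 and 5.12.6 then keep it out of both the primary and the sensitivity analysis. Only systemic embolism among these four touches the primary endpoint.

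The numerical effect is probably small. If 1-5% of all ATEs were provable only at autopsy, equally in both arms, the chance of wrongly declaring non-inferiority at the margin would go from 2.4% to 2.5-3.1% at 1,641 per arm. That rests on an assumed share and on a score-based exact test standing in for the planned one. The point merits action because the direction favours non-inferiority, the plan treats fatal bleeding differently without giving a reason, and the correction is nearly free. It does not by itself threaten the trial's conclusion.

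**What to change.** - **Section 5.10.1, item 3:** change the verification line to *intraoperative, radiologic or autopsy evidence of arterial occlusion*. The other two criteria stay.
- **Section 5.10.3:** add autopsy evidence as an accepted proof for PE, DVT and MI. For MI it should be an alternative to the marker criterion. For PE and DVT, state whether the symptom criterion still applies to a sudden death.
- **Section 5.12.1:** state that a death with an autopsy-proven ATE, adjudicated blind by the CEC, counts as an ATE event and not as an event-free death. Align the censoring rule in section 5.12.6.

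The cost is a few words in these sections and a matching instruction to the CEC, which already reviews all deaths. Sample size and patient management do not change. The limitation is that autopsy is not mandated, so only autopsied deaths are recovered. Counting deaths that the CEC attributes to ATE, MI or PE without objective proof is a separate trade of specificity for sensitivity and is not proposed here.
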